#### Rationale

- Despite the above risks, Botox has established as a safe procedure with minimal likelihood of serious side effects when done under sterile technique. The immediate risks are temporary and/or easily treated ameliorated with prompt treatment.

#### Value

- R-CECS remains a difficult-to-treat entity as established treatments are limited and outcomes are less than ideal

Please see package insert in appendix

### 2.7.2 Protection Against Risks

#### Immediate risks

- Pain during injection
  - o Barring other risks, this will be temporary and will be involved in the pre-injection consent. The needle to perform the injection will be of the smallest gage that can be reasonably considered to successfully perform the injection including visualization under US. The discomfort that can be experienced with some injections of Botox cannot be mitigated.
- Infection of injection site
  - o Sterile technique will be maintained with an assistant in the room to both assist with the injection and to monitor for sterile technique. Injection will be performed at a clinic that regularly performs injections under US guidance and has extensive experience in maintaining sterile technique.
- Bleeding following injection
  - o Subject on blood-thinning medication will not be included in the study. The gage of the needle will be relatively small and poses a minimal risk for prolonged bleeding. Should this occur, proper protocol of

- manual pressure and possible pressure bandage will be applied and the patient monitored for cessation of bleeding prior to departure from the clinic
- Swelling at injection site
  - o Subject will be counseled on proper wound care and have investigating physician contact information and rehabilitation on call physician information prior to injection should further guidance be warranted after the injection.
- Ultrasound
  - o Should abnormal findings be noted on scanning for appropriate injection location, patients will be instructed to follow up with referring provider for further work-up.

#### Long-range risks

- Lower extremity, foot, ankle weakness
  - o Should this weakness occur, the subject will have some functional dorsiflexion from these spared muscles as well as sparing the soleus for plantarflexion. If this effect does occur, the injection physician will follow up with the subject sooner than the planned 2 month follow up and can consider further treatment such as ankle foot orthosis to aid in safe ambulation at the cost of the research funding source.
- Distant spread resulting in botulism-like symptoms including muscle weakness all over body, vision problems, difficulty speaking or swallowing, trouble breathing, loss of bladder control
  - o Subject will have proper physician contact information to monitor for side effects. The risk will be explicitly discussed during written consent prior to the injection as it is a black box warning mandated by the FDA for the treating medication.
  - o Should these effects occur, subject will speak with either the investigating physician or rehabilitation physician on call. Effects will be triaged and appropriate referrals made up to and including evaluation in the emergency department.

#### Withdrawal

- Patients who wish to withdrawal from the study may do so by verbal or written request to the investigator. Or they may indicate withdrawal by failure to follow up with study protocol.

### 2.7.3 Potential Benefits to the Subjects

Given uncertainty in patient treatment benefits, current subjects may or may not experience benefit from the study though future patients may benefit from study findings.

### 2.7.4 Risk Minimization:

To avoid risks associated with injection, sterile technique will be maintained by the treating physician and assistant during the injection. The assistant will also aid the treating physician in monitoring the sterile field for violations of sterile technique. Subjects will also be given follow-up instructions and instructions for contacting appropriate physician (investigating or on call rehabilitation physician) should adverse effects occur.

## 3 Study Objectives and Purpose

- Primary Objective: To assess the efficacy of OnabotulinumtoxinA (Botox) on decreasing pain associated with R-CECS.
- Secondary Objective: To assess the safety and tolerability of Botox injections of Botox for patients with R-CECS
- Secondary Objective: To assess the ability to return to sport following injection of Botox in subjects with R-CECS

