## 2.2 Hypothesis

Hypothesis: Injection of Botox into the affected muscle group will alleviate pain associated with R-CECS.

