## 4 Study Design and Endpoints

### 4.1 General Design

- Design: Pilot study without randomization or blinding
- Please see page 6 for schematic design of trial including duration of subject participation
- Summary: Subjects will be enrolled in study at initial clinic visit by study staff at which time diagnosis of R-CECS will be established based on elevated pressure measurements in patients who have had surgical release of the affected compartments. Pressure testing will be performed outside of the clinical study and will be required to establish the diagnosis of R-CECS.

Initial clinic visit with study staff will consist of baseline measurements of ankle plantarflexion, dorsiflexion, inversion, and eversion strength using Kiio Force Sensor. The clinic visit with study staff will establish time point 0 and will consist of written consent for participation, Botox injection, and baseline UWRI. Two months following this visit, the patient will have follow up with study staff. Study staff will again measure ankle strength (ankle inversion, eversion, plantarflexion, and dorsiflexion) using the Kiio Force Sensor utilizing the same strength assessment protocol. Study staff will monitor for side effects and administer the UWRI. Telephone follow up assessment of the UWRI will be made by study staff at 4 and 6 months. For patient incentive, money will be distributed in person consisting of: \$100 at time of injection, \$50 at 2 month follow up, and \$50 following the 6 month follow up. The final payment will be mailed to the subject to an address they provide at the time of follow up.

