## **5.4 Subject Screening for Recruitment**

### **5.4.1 Subject Identification**

Potential subjects will be identified at the time of diagnosis by the investigators. Using their clinical discretion, discussion of the study will be offered alongside current standard treatments. Should the participating be interested in participation, the written consent form will be provided and clinic appointments scheduled with study staff for enrollment. Participant name and contact information will be provided to study staff by the diagnosing investigator for further contact with the study team.

Prior to enrollment, primary investigator will discuss via telephone call the timeline, interventions, goals, potential side effects, and incentive of the study. Subjects will also be screened for inclusion and exclusion criteria prior to enrollment. If more discussion is desired by potential subjects, co-investigators can contact potential subjects by telephone prior to scheduled enrollment. Eventual enrollment in the study will be elective provided the subject meets inclusion criteria.

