### **6.8 Randomization and Blinding of Study Drug**

The subjects and drug will not be blinded in this study and subjects will not be randomized into differing treatment arms.

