## 7.3 Study Visits

### 7.4.1 Screening/Baseline:

Screening and consent will be discussed with PI at clinic visit in which IMP measurement (CECS diagnosis) is taken prior to enrollment in the study. If patient is not from local community, study will be discussed over telephone prior to enrollment. Once consent is obtained, baseline force measurements and UWRI (at study clinic visit 1) will both be scheduled within 1 month of IMP measurement.

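### The primary objective asks for efficacy, but one open-label arm with no comparator can only estimate how pain changes after the injection

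*Combined protocol and SAP*

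**What the plan says.** Section 3 (Study Objectives and Purpose) gives the aim: "Primary Objective: To assess the efficacy of OnabotulinumtoxinA (Botox) on decreasing pain associated with R-CECS". Section 2.2 is equally causal: "Injection of Botox into the affected muscle group will alleviate pain associated with R-CECS". Sections 5.7.1 and 10.5 both list demonstrated efficacy as a possible reason to stop the study, although 8.4 plans no interim analysis.

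The design in section 4.1 is "Pilot study without randomization or blinding", and section 6.8 confirms that "subjects will not be randomized into differing treatment arms". The Study Summary states that there is no direct comparison.

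The primary endpoint (4.1.1) is a 2-point fall on a 0-10 pain rating with activity, recorded per leg. Section 8.2 assesses change in pain from baseline at 2, 4 and 6 months with Friedman's ANOVA. Section 8.1 is powered for a significant overall F-test on a 2-point fall (SD 1) from baseline to 6 months. It then says that 10 patients (20 legs) suffice to give preliminary effect sizes for later studies. No alpha, success rule, historical benchmark or repeated baseline is given.

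**The concern.** A change-over-time test asks whether pain differs between occasions. It does not ask why. Every patient knows that Botox was given and rates their own pain, so a placebo response enters the result in full.

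The protocol itself names other routes to lower pain. Section 2.1 says that stopping the provoking activity resolves symptoms in most cases, and section 6.7 allows over-the-counter analgesics as needed. The running items in 4.1.2 would show reduced activity descriptively, but no analysis uses them to separate it from a drug effect. Neither visit table (Tables 3 and 4) lists analgesic use.

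Two things are at stake. The objective as worded cannot be answered by these data, yet a small p-value would invite the claim. And an effect size that contains non-specific change would overstate the drug-specific difference in the later studies that 8.1 wants to inform.

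**Working it through.** **Inputs.** From 8.1: 2-point fall, SD 1, 80% power, 6 patients before inflation, 10 after. From 8.2: Friedman's ANOVA at 2, 4 and 6 months. Assumed, because the documents do not give them: alpha 0.05, the size of the non-specific fall (0.5 to 1.5 points, sustained at all three visits), and an SD of change of 1 or 2. If 8.1's SD of 1 is the SD of a single score, the SD of change is √(2(1−ρ)): 1.0 at within-patient correlation 0.5, and 1.41 at 0.

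**1. The plan's own figure.** One-way ANOVA with four occasions and a linear decline of 0, 0.67, 1.33, 2 points:
- λ = n Σ(μⱼ − μ̄)²/σ² = 6 × (1 + 0.11 + 0.11 + 1) = 13.3
- F with 3 and 20 df, critical value 3.10: power 80.2%.

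The stated 80% is reproduced with 6 independent units per occasion. The figure does not by itself show that baseline is one of the occasions: three change scores with means 0, 1, 2 give 80.5% at n=6. It is the wording of 8.1, a fall from baseline to 6 months, that implies baseline is included.

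**2. Inert injection, baseline included.** Drug effect zero, 10 patients with one value each, whole-number scores from 0 to 10, Friedman's test on four occasions (χ² with 3 df), by simulation. Repeat runs differ by about 1 to 2 percentage points. As a cross-check, a two-sided one-sample t-test on the change has noncentrality fall × √10 / SD and critical value 2.262; a fall of 1 at SD 1 gives noncentrality 3.16 and 80%.

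| Non-specific fall | Friedman, SD 1 | t-test, SD 1 | Friedman, SD 2 | t-test, SD 2 |
|---|---|---|---|---|
| 0.5 | 21% | 29% | 8% | 11% |
| 1.0 | 75% | 80% | 24% | 29% |
| 1.5 | 98% | 99% | 48% | 56% |

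Treating 20 legs as independent raises the Friedman figures to 46%, 98% and about 100% (SD 1), or 15%, 49% and 85% (SD 2).

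**3. Inert injection, three change scores only.** Subtracting the same baseline from a patient's three follow-up scores leaves their ranks unchanged, and so does a constant fall. The test then sees only differences among visits and rejects about 5% of the time, whatever the size of a sustained fall.

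**4. The 2-point endpoint.** With an inert injection and a 1-point non-specific fall, about 31% (SD 1) to 40% (SD 2) of legs would show a fall of at least 2 points. With no fall at all the figures are about 8% and 23%.

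**5. What the design can deliver.** The 95% interval for mean change has half-width 2.262 × SD/√10: 0.72 points at SD 1, 1.43 at SD 2.

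**6. Consequence for a later controlled trial.** n per arm = 2(1.96 + 0.84)²(SD/Δ)². At SD 1, Δ=2 gives 3.9, so 4 per arm; Δ=1 gives 15.7, so 16. If half of an observed 2-point fall were non-specific, sizing on the whole fall would plan a quarter of the patients needed.

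**The case against.** The study is openly a pilot. Section 8.1 says that its size serves preliminary effect sizes, the Study Summary discloses that there is no comparison, and 2.7.3 admits that benefit is uncertain. This lowers the stakes, but section 3, 2.2, 5.7.1 and 10.5 are not limited to that purpose.

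A reader might infer that the plan tests change against zero and will therefore declare an inert injection effective. The documents do not support that. On a literal reading of 8.2 the test compares the three changes with each other, and there is no alpha or rule for declaring success. The percentages also count any p<0.05 and depend on an assumed fall, so they show how the test behaves and say nothing about what these patients will do.

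A reader might also treat late surgical recovery and regression to the mean as established biases. Both are only plausible. Inclusion criterion 4 sets no minimum interval since release, but it requires raised pressure after surgery, so these patients have recurrent disease. Section 5.4.1 says "Potential subjects will be identified at the time of diagnosis by the investigators", but eligibility uses pressure and sets no pain threshold.

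Finally, a control arm might seem the obvious answer. Ten patients split 5:5 would have 79% power for a 2-point difference but 29% for 1 point (SD 1, exact t), so asking for one within this pilot would be disproportionate. None of these arguments allows a fall in pain to be attributed to Botox.

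**Conclusion.** The concern holds as a mismatch between the objective and the design. The trial can estimate change in pain after injection but cannot assess efficacy. With baseline in the Friedman test, an assumed non-specific fall of 1 point would give p<0.05 in about a quarter (SD 2) to three quarters (SD 1) of trials of an inert injection. With change scores only, the rate stays near 5% and the test does not address overall improvement at all. These figures rest on alpha 0.05, a sustained fall of assumed size and one value per patient. A false efficacy claim is a risk that the wording invites, not a result that the plan makes certain.

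**What to change.** 1. Reword 2.2 and the primary objective in section 3 along these lines: *to estimate the change in pain with activity after a Botox injection*.
2. In 8.2, state that the change will be reported with a 95% confidence interval and that change from baseline will not be presented as evidence of efficacy.
3. In 8.2, state that baseline is one of the repeated measures in the Friedman test.
4. Reconcile the demonstrated-efficacy wording in 5.7.1 and 10.5 with the new objective, and with the absence of an interim analysis in 8.4.

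These cost only text and change no visit, endpoint or sample size. The downside is a weaker headline claim.

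Optional: take a second pain score before injection. It would show short-term drift over at most a month, since 7.4.1 says "Once consent is obtained, baseline force measurements and UWRI (at study clinic visit 1) will both be scheduled within 1 month of IMP measurement". It cannot measure placebo response, and it needs signed consent earlier than visit 1, where 5.6.1 and Table 4 place it. The date of the last fascial release could also be recorded as a descriptive variable; splitting 10 patients by it would not be informative.

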## 4 Study Design and Endpoints

### 4.1 General Design

- Design: Pilot study without randomization or blinding
- Please see page 6 for schematic design of trial including duration of subject participation
- Summary: Subjects will be enrolled in study at initial clinic visit by study staff at which time diagnosis of R-CECS will be established based on elevated pressure measurements in patients who have had surgical release of the affected compartments. Pressure testing will be performed outside of the clinical study and will be required to establish the diagnosis of R-CECS.

Initial clinic visit with study staff will consist of baseline measurements of ankle plantarflexion, dorsiflexion, inversion, and eversion strength using Kiio Force Sensor. The clinic visit with study staff will establish time point 0 and will consist of written consent for participation, Botox injection, and baseline UWRI. Two months following this visit, the patient will have follow up with study staff. Study staff will again measure ankle strength (ankle inversion, eversion, plantarflexion, and dorsiflexion) using the Kiio Force Sensor utilizing the same strength assessment protocol. Study staff will monitor for side effects and administer the UWRI. Telephone follow up assessment of the UWRI will be made by study staff at 4 and 6 months. For patient incentive, money will be distributed in person consisting of: \$100 at time of injection, \$50 at 2 month follow up, and \$50 following the 6 month follow up. The final payment will be mailed to the subject to an address they provide at the time of follow up.

#### 4.1.1 Primary Study Endpoints

1. Decrease in pain by 2 points on 0-10 numeric rating scale with activity, measured in each leg

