### Study Summary

## ONABOTULINUMTOXINA (BOTOX) EFFECT ON PAIN AND FUNCTION IN RECURRENT CHRONIC EXERTIONAL COMPARTMENT SYNDROME: A PILOT STUDY

Title	OnabotulinumtoxinA (Botox) effect on pain and function in recurrent chronic exertional compartment syndrome: a pilot study
Short Title and Precis	Botox for the treatment of recurrent chronic exertional compartment syndrome
Methodology	Open label pilot study
Study Duration	2 years
Study Center(s)	University of Wisconsin Hospitals and Clinics
Objectives	Determine effect of Botox on pain and function using the University of Wisconsin Running Index
Number of Subjects	10 subjects consisting of 20 legs
Diagnosis	Recurrent chronic exertional compartment syndrome (R-CECS)
Main Inclusion Criteria	Patients greater than 18 years of age with diagnosis of R-CECS
Main Exclusion Criteria	Diagnosis other than CECS
Study Product, Dose, Route, Regimen	Botox (reconstituted at 100 units/mL) to be injected under standard palpatory technique into the affected lower leg compartment. Dosage will be based upon the affected muscles
FDA status of product	FDA approved
Duration of administration	6 month follow up time after injection of medication. Typical duration of action of Botox is 10-12 weeks
Reference therapy	No direct comparison
Statistical Methodology	Using a one-way ANOVA and assuming independence of leg scores for each patient, we will have 80% power to detect an overall significant F-test (assuming a 2 (SD=1) point decrease in pain score from baseline to 6 months) with n=6 patients (e.g. 12 legs). Accounting for potential drop-out (15%) and, additionally, adjusting for non-parametric analyses, n=10 patients (e.g 20 legs) will be sufficient to provide preliminary effect sizes at each time point which will help inform power analyses for studies planned beyond this pilot study.

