### **2.6 Dose Rationale**

Dosing considerations were made in looking at previous studiesxv,xviii as well as medical expertise of the investigators. A previous studyxviii have injected 40 units (20 proximal and 20 distal) into the each the TA, extensor digitorum longus, and extensor hallucis longus. Our protocol changes this dosing to the following:

- 50 units total (25 proximal and 25 distal) into the TA for anterior symptoms
- 50 units in to the peroneal longus for the lateral compartment
- 50 units into each the medial and lateral gastrocnemius for superficial posterior symptoms
- 50 units into the tibialis posterior for deep posterior symptoms

We chose a dosage on the low end recommended by the previous studies for hypertonicity in the respective muscles in conjunction with the investigator's clinical expertise. To ensure placement of the medication into the proper muscle, we will be using standardized palpatory techniques as is common in Botox injections for spasticity. A single injection will be performed in this study as previous studies have shown prolonged pain relief despite a known

duration of action of the medication to be 2-6 months to help determine the duration of relief in this diagnosis. Given this duration of action, most side effects associated with muscle weakness are temporary and resolve over time.

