### **6.4 Route of Administration**

- Dose will be determined based upon patient location of symptoms as follows:
  - - 50 units total (25 proximal and 25 distal) into the TA for anterior symptoms
  - - 50 units in to the peroneal longus for the lateral compartment
  - - 50 units into each the medial and lateral gastrocnemius for superficial posterior symptoms
  - - 50 units into the tibialis posterior for deep posterior symptoms
- Treatment duration: Established duration of action on muscular weakness of other uses of Botox is between 2 and 4 months. Given this novel treatment, duration of action in our study is unknown.
- Expected side effects include:
  - Weakness in the muscle injected
  - Injection site pain
  - Injection site bleeding

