### 8 Study Analysis

#### 8.1 Sample Size Determination

Using a one-way ANOVA and assuming independence of leg scores for each patient, we will have 80% power to detect an overall significant F-test (assuming a 2 (SD=1) point decrease in pain score from baseline to 6 months) with n=6 patients (e.g. 12 legs). Accounting for potential drop-out (15%) and, additionally, adjusting for non-parametric analyses, **n=10 patients (e.g 20 legs) will be sufficient** to provide preliminary effect sizes at each time point which will help inform power analyses for studies planned beyond this pilot study.

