#### 8.2 Statistical Methods

Basic descriptive statistics, means (SD) and medians (IQR) for continuous variables and frequencies (percentages) for categorical variables will be used to summarize patient outcomes. For the primary outcome, change in pain (from baseline on 0-10 numeric rating scale) will be assessed at each time point (2,4,6 months) using Friedman's ANOVA. Friedman's ANOVA is the non-parametric analog to one-way repeated measures ANOVA and is often

used for ordinal outcomes. If necessary and feasible, GEE models will be constructed to further assess changes in pain while accounting for intra-subject correlation. Secondary endpoints utilizing the UWRI will also be assessed in this manner. Change in strength outcomes at baseline and 2 months will be assessed using Wilcoxon signed rank tests or, if necessary, linear mixed effects models for repeated measures, to account for intra-subject correlation (left and right legs).

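### The 2-point primary endpoint names no visit, and the planned Friedman test never evaluates it, so the plan as written gives no result for its own primary endpoint

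*Combined protocol and SAP*

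**What the plan says.** - **Endpoint (4.1.1).** The single primary endpoint reads "Decrease in pain by 2 points on 0-10 numeric rating scale with activity, measured in each leg". No visit is given, and no proportion of legs or subjects that must reach it.
- **Analysis (8.2).** The primary outcome is handled as follows: "change in pain (from baseline on 0-10 numeric rating scale) will be assessed at each time point (2,4,6 months) using Friedman's ANOVA". A second step is conditional: "If necessary and feasible, GEE models will be constructed to further assess changes in pain while accounting for intra-subject correlation". Neither sentence mentions 2 points, a responder or a primary visit. A general sentence promises means, medians and frequencies for outcomes, but defines no responder variable.
- **Sizing (8.1, repeated in the Study Summary).** The calculation assumes a 2-point fall with SD 1, described as a "point decrease in pain score from baseline to 6 months", and an overall F-test. It adds that 10 patients will supply preliminary effect sizes at each time point for planning later studies.
- **Duration of action.** The Study Summary says "Typical duration of action of Botox is 10-12 weeks". Section 6.4 says "Established duration of action on muscular weakness of other uses of Botox is between 2 and 4 months", and 6.6 gives the same range. Section 2.6 puts the "duration of action of the medication to be 2-6 months". Section 6.4 adds that duration in this use is unknown.

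**The concern.** A primary endpoint should fix the measure, the time and the summary that answers the question. Here the measure is fixed, the time is absent, and the planned test answers something else: whether pain scores differ somewhere across visits. A Friedman p-value, large or small, does not say whether pain fell by 2 points.

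Someone will therefore have to choose the visit and the counting rule after the data are in, in a trial with no control arm and no blinding, where prespecification is one of the few protections available. The figure carried into the next study's power calculation would then have no defined time point. Nor do the documents suggest an obvious default visit, because the sizing uses 6 months while most of the stated durations of action end earlier.

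**Working it through.** **1. The plan's own figure.** Inputs from 8.1: a 2-point decrease, SD 1, 80% power, one-way ANOVA, 6 patients. Assumed, because not stated: alpha 0.05, four time points (0, 2, 4, 6 months), a linear decline.

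- Means: 0, -0.67, -1.33, -2; grand mean -1.
- Sum of squared deviations: 1 + 0.111 + 0.111 + 1 = 2.222.
- Noncentrality with 6 observations per time point: 6 × 2.222 / 1² = 13.33, on 3 and 20 degrees of freedom.
- Power: 0.802. With 5 per time point it is 0.695, so 6 is the smallest number reaching 80%.

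The stated figure reproduces. In it, 6 months is the end of an assumed trajectory for an overall test, and SD 1 acts as the SD of scores within a time point.

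**2. Does the planned test evaluate the endpoint?** The wording of 8.2 allows two versions.

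- *Change scores at the three follow-up visits, as worded.* Subtracting a subject's baseline from all three scores leaves their ranking unchanged, so the baseline drops out. The test then asks only whether 2, 4 and 6 months differ from one another. For a sustained fall of 2 points (true means -2, -2, -2; SD 1, independent scores, n = 10), simulation gives rejection in about 4-5% of trials, which is the nominal error rate.
- *Baseline included as a fourth level.* The test can detect an effect: for a sustained 2-point fall under the same assumptions the simulated power is about 0.96. It still rejects or not without reference to whether any leg fell by 2 points, and it does not point to a visit.

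Neither version yields a result for the endpoint in 4.1.1.

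**3. What an open visit does to a 2-point count.** Take a leg with no true change, a normal change score with SD s, and correlation r between the changes at any two visits.

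- One named visit: P = Φ(-2/s).
- Any of three visits: P = 1 - P(all three changes > -2), by simulation.

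| SD of change (assumed) | One named visit | Any of three, r = 0.7 | Any of three, r = 0.5 | Ratio |
|---|---|---|---|---|
| 1 | 2.3% | 5.0% | 5.8% | 2.2-2.5 |
| 1.5 | 9.1% | 17.5% | 20.1% | 1.9-2.2 |
| 2 | 15.9% | 28.1% | 32.2% | 1.8-2.0 |

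Section 8.1 does not say that its SD of 1 is an SD of change. If scores have SD 1 at each visit and correlation c with baseline, the SD of change is √(2(1 - c)): 1.0 at c = 0.5 and 1.41 at c = 0. The SD of 2 is an assumption with no source in the documents.

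**4. Visits against the stated durations.** 10-12 weeks is 70-84 days, or about 2.3-2.8 months at 30.4 days per month.

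| Stated duration | 2 months | 4 months | 6 months |
|---|---|---|---|
| 10-12 weeks (Study Summary) | within | beyond | beyond |
| 2-4 months (6.4, 6.6) | lower end | upper end | beyond |
| 2-6 months (2.6) | lower end | within | upper end |

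Two months is the only visit beyond none of the stated durations. Six months is the only time the sizing uses.

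**The case against.** The strongest reply is that this is an uncontrolled pilot meant to estimate effects at every visit. It plans one omnibus test, so no claim at a favourable visit is planned, and a count that is not planned cannot be inflated. The 2 points may also be a target mean decrease, matching 8.1, rather than a responder threshold. Most of this is fair. The percentages above describe a rule someone might adopt, not one the plan contains. But the ambiguity between mean and proportion is itself part of the gap. On the mean reading, the general descriptive summary would give a mean at each visit, with no nominated visit and no confidence interval.

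Two stronger readings are tempting and are not supported.

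- *The endpoint will be judged after the effect has ended.* The stated durations concern drug action, in 6.4 specifically muscle weakness in other uses. Section 2.1 reports pain relief at 11 and 14 months in case reports, 2.6 refers to prolonged relief, and 6.4 calls the duration here unknown. Relief may outlast drug action.
- *An effect that wore off would read as failure.* No section plans a 6-month-only verdict. With means 0, -2, -1, 0 and SD 1, the F-test in 8.1 has power 0.885 at n = 6. A Friedman test with baseline as a fourth level has about 0.95 at n = 10 (independent scores, alpha 0.05 assumed).

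It is also fair that 2 months is one defensible choice and not one that the documents imply.

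**Conclusion.** The point holds on the text. The primary endpoint has no visit, the planned analysis does not evaluate it, and the one time tied to the 2 points appears only in the sizing. That part needs no assumption.

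The size is conditional. If a 2-point fall at any visit were counted, an unchanged leg would qualify roughly 1.8 to 2.5 times as often as at one named visit, given normal changes, SDs of 1 to 2 and correlations of 0.5 to 0.7, all assumed. The finding that Friedman's test on change scores misses a sustained fall rests on the literal wording of 8.2 and disappears if baseline is entered as a level, but the missing 2-point result remains either way.

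This should be corrected before analysis. It does not invalidate the design or the sample size.

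**What to change.** - **4.1.1:** name one primary visit before any analysis, and say that the criterion is a decrease of at least 2 points from baseline. The sponsor should choose and justify the visit: 2 months is the only one inside every stated duration of action, and 6 months matches the current sizing.
- **8.1 and Study Summary:** use the same visit. If it is not 6 months, restate the sizing assumption.
- **8.2:** report the number and proportion of subjects meeting the criterion at that visit with an exact 95% CI, stating how a subject with two treated legs is counted (for example both legs, either leg, or a designated leg). Give the mean change with its CI alongside. Report the other two visits in the same way, as secondary measures of how long relief lasts.
- **Study Summary, 2.6, 6.4 and 6.6:** reconcile the statements of duration of action.

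The cost is protocol wording and one table, with no added visits or patients; two visits become secondary but are still reported in full. One check is needed: Tables 3 and 4 list the UWRI at each visit but do not list a 0-10 pain score for each leg, so the team should confirm that this score is collected at the chosen visit.
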